3.1 Flow of participants

Participant flow will be described via a flowchart (see **Figure F1**). Follow-up will last 12 months with follow-up visits planned at 5 weeks, 3 months, 6 months and 12 months post-randomisation.

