3.6 Safety population

The safety population for the main trial analyses will consist of **all** randomised patients, excluding patients withdrawn who were unwilling for data collected to be used.

Participants will be grouped according to the treatment allocated and events in participants who received the alternative treatment (e.g. VATS received by participant randomised to open or vice versa), did not undergo a lobectomy, or received no treatment will be detailed in footnotes.

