5.2 Secondary outcomes

1. Time from surgery to hospital discharge

Both time from surgery until first fit for discharge, and time from surgery until hospital discharge will be described. Time from surgery until hospital discharge will be compared between groups.

New variable	Rules
Time from surgery to hospital discharge	= (Discharge date – operation date)
Fit for discharge	YES: if satisfactory mobility = YES AND pain under control with oral analgesia = YES AND satisfactory Hb & electrolytes = YES AND satisfactory chest X-ray = YES (or satisfactory on a previous day and not necessary to repeat) AND free from complications requiring treatment = YES NO: if satisfactory mobility = NO OR pain under control with oral analgesia = NO OR satisfactory Hb & electrolytes = NO OR satisfactory chest X-ray = NO (or not done and not previously satisfactory) OR free from complications requiring treatment = NO MISSING: otherwise
Time from surgery to fit for discharge	= (First day fit for discharge – operation date)

2. Pain scores in the first two days post-surgery

Pain scores are collected at baseline (prior to surgery), day one post-surgery and day two post-surgery. Pain scores are collected directly on CRFs using the visual analogue scale (VAS) and so no derivation is required.

3. Adverse health events to 1 year

All adverse events occurring at any time during the 12 month follow-up period will be reported.

New variable	Rules
Maximum intensity of SAE (CTCAE)	Maximum of CTCAE variable on initial SAE form and all follow-up SAE forms

4. Proportion and time to uptake of adjuvant treatment

The proportion of patients receiving adjuvant treatment at any time during the 12 month follow-up period will be described. The time to uptake of adjuvant treatment will be calculated as follows:

New variable	Rules
Uptake of adjuvant treatment	YES: if at any study visit, chemotherapy or radiotherapy started = YES NO: if at all attended study visits, chemotherapy and radiotherapy started = NO MISSING: otherwise
Time to uptake of adjuvant therapy	= (Earliest chemotherapy/radiotherapy start date - randomisation date)

5. Proportion of patients upstaged to pN2 disease after the procedure

The proportion of patients upstaged to pathological N2 disease following surgery will be derived as follows:

New variable	Rules

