6.3 Safety data

Adverse events (AEs) and serious adverse events (SAEs) occurring in the study period for all patients in the safety population will be tabulated as per **Table T19 and T20**.

Table T19 summarises AEs and SAEs experienced during the period from randomisation to hospital discharge. Such events are captured via the study CRFs.

Table T20 summarises SAEs experienced during the follow-up period from hospital discharge to 12 months post-randomisation.

All events will be coded using MedDRA and reported according to this classification system. The difference in the proportion of patients with any adverse event and with any serious adverse event (according to the standard GCP definition of serious) will be reported with a 95% CI. The outcome of serious events (alive or died following the event) will be described. The difference in proportion of patients experiencing an event (serious or non-serious) in each MedDRA system organ class group (SOC) will also be reported with 95% CIs for each SOC with events in both groups and at least five events in total across the two groups. These estimates will be displayed in a Forest plot (see Figure F9). P-values will not be included.

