APPENDIX A: SKELETON TABLES AND FIGURES

The following summarises the planned outputs:

Section	Outputs
Section 1 Population	Tables, figures and listings detailing the study population Figure F1 Flow of participants Figure F2 Predicted and actual recruitment Table T1 Protocol deviations Table T2 Details of conversions from VATS to open surgery Table T3 Withdrawals
Section 2 Baseline and intra-operative data	Summary tables of demographic and operative information Table T4 Baseline demographic and clinical characteristics Table T5 Operative details
Section 3 Additional descriptive information	Summary tables of additional descriptive information Figure F3 Pathology flow chart Table T6 Patient blinding at 2 days post-surgery Table T7 Patient blinding at discharge Table T8 Nurse blinding at discharge Table T9 Nurse blinding at 5 weeks Table T10 Nurse blinding at 12 months
Section 4 Primary and secondary outcome data	Summary data and treatment estimates for primary and secondary outcomes Table T11 Primary outcome Figure F4 Primary outcome Table T12 In-hospital secondary outcomes Table T13 Additional secondary outcomes Table T14 Pain scores in the first two days post-surgery Figure F5 In-hospital secondary outcomes Figure F6 Mean ratios of in-hospital analgesia Figure F7 Additional secondary outcomes Table T15 QLQ-C30 global health status/functional scale scores Figure F8 Global health status over time Table T16 QLQ-C30 symptoms scale scores Table T17 QLQ-LC13 Table T18 EQ5D Table T19 Adverse events and serious adverse events in-hospital Table T20 Serious adverse events during follow-up Table T21 Sensitivity analysis of primary outcome excluding patients with benign disease Figure F9 Adverse events in-hospital Figure F10 Subgroup analysis of pain score Figure F11 Sensitivity analysis of survival outcomes adjusting for pathological disease stage Figure F12 Exploratory analysis of in-hospital pain score by of thoracotomy performed Figure F13 Exploratory analysis of QLQ-C30 pain score by type of thoracotomy performed Table T22 Pain scores by number of port sites Table T23 Exploratory analysis comparing pain scores by number of port sites Table T24 Exploratory analysis comparing length of stay by number of port sites

Figure F1 Flow of participants

Notes:

¹ Patients may be ineligible for more than one reason

Benign patients are only followed-up to 5 weeks post-randomisation; allocated to open (n=xx), allocated to VATS (n=xx)

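### Table T20 keeps benign patients, followed for only 5 weeks, in the denominator of a discharge-to-12-month SAE percentage, which is therefore somewhat too low in both arms

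*SAP*

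**What the plan says.** Four places in the SAP bear on this.

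- **Appendix A, Figure F1, notes.** "Benign patients are only followed-up to 5 weeks post-randomisation". The note leaves room for the number of such patients in each arm. This is a planned end of follow-up, not dropout.
- **Section 3.6.** The safety population is all "randomised patients, excluding patients withdrawn who were unwilling for data collected to be used". Benign disease is not a reason for exclusion, and patients are grouped by allocated treatment.
- **Section 6.3.** AEs and SAEs "occurring in the study period for all patients in the safety population will be tabulated as per" Tables T19 and T20. For the second of these, "Table T20 summarises SAEs experienced during the follow-up period from hospital discharge to 12 months post-randomisation". The T20 shell has events/patients and a percentage for each randomised arm. It has no column for number under follow-up or person-time, and no footnote on benign patients.
- **Sections 3.1 and 5.2 (item 3).** The general text makes no exception for benign patients: "Follow-up will last 12 months with follow-up visits planned at 5 weeks, 3 months, 6 months and 12 months post-randomisation", and "All adverse events occurring at any time during the 12 month follow-up period will be reported".

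Benign patients are removed only in an additional analysis of the primary outcome (sections 3.5 and 6.2.6). Adverse events to one year are a listed secondary outcome (section 2.4, item 3).

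**The concern.** A percentage for a stated period is read as the share of patients who had an event in that period. In T20 some patients are observed to 12 months and others, by design, to week 5 only. After week 5 the second group is in effect counted as event-free, although nobody looked.

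The SAP deals with unequal follow-up elsewhere: section 6.2.2 censors overall survival, disease-free survival and time to adjuvant treatment at the last visit. T20 has no such device, and the missing-data rules in section 6.2.8 do not address safety counts. At stake is the absolute level of post-discharge SAEs reported for each operation.

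**Working it through.** The SAP states no SAE rate and no benign share, so there is no figure of its own to reproduce. The direction of the error follows from the text; its size needs assumptions.

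**Inputs from the SAP**

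- Benign follow-up ends at 5 weeks, against a 12-month window: 35/365 = 9.6% of the year.
- T20 denominator: the safety population by arm (sections 3.6 and 6.3).
- Planned size 498, randomised 1:1 (sections 3 and 3.2): 498/2 = 249 per arm.

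**Formula**

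Let b be the benign share of an arm, q the 12-month post-discharge SAE risk of the other patients, and p5 and p12 the benign patients' own risks by week 5 and by 12 months.

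- Percentage with complete follow-up: (1 − b) × q + b × p12
- Percentage that T20 would show: (1 − b) × q + b × p5
- Shortfall: b × (p12 − p5)

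The risk q cancels. Only the benign patients' own later risk matters. The shortfall is above zero whenever an arm contains benign patients with some risk of a first post-discharge SAE after week 5.

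**Size, for assumed values**

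| b (patients of 249) | p5 5%, p12 15% | p5 10%, p12 30% | p5 15%, p12 40% |
|---|---|---|---|
| 2% (5) | 0.2 points | 0.4 | 0.5 |
| 5% (12) | 0.5 | 1.0 | 1.25 |
| 10% (25) | 1.0 | 2.0 | 2.5 |
| 20% (50) | 2.0 | 4.0 | 5.0 |

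If the other patients have the same 12-month risk (q = p12), the middle column means that T20 shows 29.6%, 29.0%, 28.0% and 26.0% where complete follow-up would give 30%. On that same assumption the relative understatement over the whole grid is about 1% to 13%.

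**Lower later risk in benign patients.** With b = 10% and p5 = 5%, a p12 of 15% gives 0.10 × 10 = 1.0 point, and a p12 of 10% gives 0.10 × 5 = 0.5 points.

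**Effect on the comparison when b is equal in both arms.** Assume true risks of 35% (open) and 30% (VATS), week-5 risks of 12% and 10%, and b = 10%.

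- Open: 0.9 × 35 + 0.1 × 12 = 32.7%
- VATS: 0.9 × 30 + 0.1 × 10 = 28.0%
- The difference is 4.7 points instead of 5.0, and the ratio 0.856 instead of 0.857.

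**The case against.** The strongest reply is that T20 is a descriptive table. It has no effect estimate, confidence interval or p-value. The safety outcomes compared by model are any AE and any SAE in hospital (section 6.2.2 and Table T12), and Figure F9 is also titled as in-hospital. Those outcomes are complete for benign patients. The benign counts by arm will appear with Figure F1, and section 1.4 lets table layouts change. All of this stands. It limits the consequence to a descriptive percentage but does not correct that percentage: T20 does not direct the reader to the Figure F1 note, and the denominator is fixed by the text of sections 3.6 and 6.3, not by the layout.

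A reader might infer three stronger things that the SAP does not support.

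- **Bias between arms.** Benign status is confirmed at or after surgery, so one might expect its share to depend on the arm. But the lesion's nature is settled before randomisation, which balances it in expectation, and the SAP describes no mechanism for different detection. A chance gap such as 8% against 14% is about 2.1 standard errors at 249 per arm. With risks of 30% by 12 months and 5% by week 5, it would move the arms to 28.0% and 26.5%. That 1.5-point gap compares with a 95% confidence half-width of about 8 points.
- **That patients who die are miscounted in the same way.** They are not. A patient who has died has no later events to miss and belongs in the denominator of a crude incidence.
- **That the full-follow-up patients' risk is the right benchmark.** That assumes benign patients carry the same later risk, for which the SAP offers nothing.

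**Conclusion.** The point holds as a small, real fault in one descriptive table. Followed as written, the plan reports a discharge-to-12-month SAE percentage that is too low in both arms by b × (p12 − p5). Over the assumed ranges this is about 0.2 to 5 points, towards the lower end if few patients are benign or their later risk is low. Every number in that range is an assumption; the direction is not.

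Neither the primary outcome nor the modelled in-hospital AE and SAE outcomes change. One matter is open: section 6.3 promises a difference with 95% CI in the proportion with any SAE and does not name the period. The planned outputs point to the hospital stay. If follow-up was meant to be included, the same denominator problem reaches that estimate.

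**What to change.** In section 6.3 and Table T20:

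1. Report discharge to 5 weeks on the whole safety population.
2. Report 5 weeks to 12 months on patients with planned follow-up beyond 5 weeks, showing the number under follow-up by arm. Alternatively, give one cumulative incidence of first post-discharge SAE, censored at end of follow-up, with death handled as a competing event and not as censoring.
3. Footnote the number of benign patients by arm, and state the 5-week exception where sections 3.1 and 5.2 (item 3) describe 12 months of follow-up.
4. Say which period the any-SAE difference in section 6.3 covers. If it includes follow-up, use the same denominator there.

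The cost is a few sentences and one table split, with no new data collection. The drawback is that the later period rests on a smaller group that is no longer all randomised patients, for example about 224 of 249 per arm if 10% are benign (249 − 25). The table should say so.

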3. STUDY POPULATION

The study population is all patients aged ≥ 16 years of age who have been referred by the multi-disciplinary team (MDT) for lung resection for known or suspected lung cancer. Eligibility criteria are as inclusive as possible to promote the applicability of the evidence obtained during the trial. For specific inclusion/exclusion criteria see **Figure F1**.

Recruitment over time against targets will be presented overall (**Figure F2**).

The planned sample size for the VIOLET study is 498 patients. This sample size would be sufficient to detect a difference of 0.25 standard deviations in physical function between the VATS and open groups with 90% power and 5% significance (2-tailed). The total sample size will allow for a 20% dropout at one year.

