3.2 Randomisation

Patients are randomised (1:1 ratio) to either VATS lobectomy or open lobectomy. Randomisation will be stratified by study centre and minimised by surgeon. Randomisation will take place within one week of the planned operation date, once eligibility has been confirmed and consent given. The randomisation will take place using a secure password protected internet-based system.

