6.2.2 Analysis models

All outcomes listed in the study protocol will be presented as per the template tables **Table T11 to T18**. General methods of presentation and assessing treatment effects are outlined below. For all treatment comparisons, the open lobectomy group will be the reference group. Details specific to each outcome are described as appropriate.

Each outcome will be considered under a certain data type, as outlined in the table below:

Date type	Outcomes
Binary	Proportion of patients receiving adjuvant treatment Proportion of patients who undergo complete resection during the procedure Proportion of patients who experience prolonged incision pain Any in-hospital adverse event Any in-hospital serious adverse event
Categorical	Proportion upstaged to pN1 disease after the procedure Proportion upstaged to pN2 disease after the procedure
Time to event	Time from surgery to hospital discharge Time to uptake of adjuvant treatment Overall survival Disease-free survival
Longitudinal	Physical function (primary) Pain scores in the first two days post-surgery HRQoL (QLQ-C30, QLQ-LC13, EQ5D)

Each type of data will be summarised and compared between the groups according to the following:

- **Binary outcomes** will be presented as numbers and percentages of patients in each treatment group. Outcomes will be compared between treatment groups using generalised linear models, with treatment comparison estimates presented as adjusted risk ratios (RR) and risk differences (RD) with 95% confidence intervals (95% CI). Formal statistical comparisons of treatment effects will only be performed if more than ten patients in total experience the outcome (with at least one event in each treatment group).
- **Categorical outcomes** will be presented as numbers and percentages of patients in each treatment group in each category. Outcomes will be compared between treatment groups using multinomial logistic regression, with treatment comparison estimates presented as adjusted RR and 95% CI.

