8. AMENDMENTS TO THE SAP

[figure not shown]
Previous version	Previous date	New version	New date	Brief summary of changes
1.0	04/07/2019	2.0	11/11/2019	
Addition of the outcome upstaging to pN1 at the request of the chief investigator.
 
Updating analysis models section to state risk ratios and risk differences will be presented instead of odds ratios for binary outcomes.
 
Addition to safety data section to state all events will be MedDRA coded and the difference in proportion of patients experiencing an event in each MedDRA system organ class group will be reported.
 
Update to adjustment in models section to remove adjustment for analgesia in pain score models as it was decided analgesia lay on the causal pathway and may therefore lead to biased estimates. Analgesia will be summarised by group instead.

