Table T14 Pain scores in the first two days post-surgery

Outcome	Randomised to open (n=XX)		Randomised to VATS (n=XX)		Effect (95% CI)	p-value
	Mean/Median	SD/IQR	Mean/Median	SD/IQR		
Pain score	Baseline					
	Day 1 post-surgery				MD/GMR	
	Day 2 post-surgery				MD/GMR	
Test for treatment*time interaction						
Overall treatment effect estimate					MD/GMR	

Analyses are adjusted for operating surgeon and centre

Figure F5 In-hospital secondary outcomes

[figure not shown]
[figure not shown]

Figure F6 Mean ratios of in-hospital analgesia

Notes: point estimate is ratio of mean daily dose of each analgesia in each group. 95% CI calculated by using bootstrap estimation with 10,000 replications to estimate the standard error of the mean ratio

Figure F7 Primary outcome and post-discharge secondary outcomes

[figure not shown]

Table T15 QLQ-C30 global health status/functional scale scores

Outcome		Randomised to open (n=XX)		Randomised to VATS (n=XX)		Effect (95% CI)	p-value
		Mean/Median	SD/IQR	Mean/Median	SD/IQR		
Global health status/QoL	Baseline						
	2 weeks					MD/GMR	
	5 weeks					MD/GMR	
	3 months					MD/GMR	
	6 months					MD/GMR	
	12 months					MD/GMR	
Test for treatment*time interaction							
Overall treatment effect estimate						MD/GMR	
Role functioning	Baseline						
	2 weeks					MD/GMR	
	5 weeks					MD/GMR	
	3 months					MD/GMR	
	6 months					MD/GMR	
	12 months					MD/GMR	
Test for treatment*time interaction							
Overall treatment effect estimate						MD/GMR	
Emotional functioning	Baseline						
	2 weeks					MD/GMR	
	5 weeks					MD/GMR	
	3 months					MD/GMR	
	6 months					MD/GMR	
	12 months					MD/GMR	
Test for treatment*time interaction							
Overall treatment effect estimate						MD/GMR	
Cognitive functioning	Baseline						
	2 weeks					MD/GMR	
	5 weeks					MD/GMR	
	3 months					MD/GMR	
	6 months					MD/GMR	
	12 months					MD/GMR	
Test for treatment*time interaction							
Overall treatment effect estimate						MD/GMR	
Baseline							

Social functioning	2 weeks	MD/GMR
	5 weeks	MD/GMR
	3 months	MD/GMR
	6 months	MD/GMR
	12 months	MD/GMR
Test for treatment*time interaction		
Overall treatment effect estimate		

Notes: higher scores indicate higher levels of functioning
Analyses are adjusted for operating surgeon and centre

Figure F8 Global health status over time

[figure not shown]

Table T16 QLQ-C30 symptom scale scores

Outcome		Randomised to open (n=XX)		Randomised to VATS (n=XX)		Effect (95% CI)	p-value

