APPENDIX B: IN-HOSPITAL ANALGESIC RATIOS

Mean ratios of analgesia received throughout the hospital stay will be summarised (Figure F6). Each analgesic will be summed for the duration of the hospital stay and the final score will be total dose (mg) if received intra-operatively or average daily dose (mg/day) if received post-operatively. Average daily dose will be calculated by dividing the total dose (mg) for the entire hospital stay by the total number of days each analgesia was received. Analgesic agents will be combined into groups where possible. If less than 5% of the entire cohort received an analgesic agent, then this analgesic will be excluded from the summary figure and will be tabulated by group instead.

Analgesics will be grouped as follows:

1. Intra-operative local anaesthetic infusions
 - Intercostal blocks
 - Paravertebral blocks
 - Paravertebral catheter
2. Post-operative local anaesthetic infusions
 - Intercostal blocks
 - Paravertebral blocks
 - Paravertebral catheter
3. Epidurals
 - Intra-operative epidural
 - Post-operative epidural
4. PCA (morphine equivalents)
5. Opiates (morphine equivalents)
6. Ibuprofen
7. Diclofenac
8. Gabapentin
9. Paracoxib
10. Paracetamol
11. Pregabalin
12. Lidocaine patches (patches/day)

Morphine equivalents

All analgesic doses will be converted to mg before converting to their morphine equivalent dose. Morphine equivalent daily dose will be calculated as:

$$= \text{current dose} \times \text{conversion factor}$$

The conversion factors used will be as specified by the Royal College of Anaesthetists: Dose Equivalent and Changing Opioids. ⁽¹⁾ Morphine equivalents will only be calculated for those analgesic medications for which a morphine equivalent is present and specified in the guidelines.

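### Figure F6 sets its 95% CI from a standard error of the raw dose ratio, so for less-used analgesics the interval errs mainly in one direction (minor)

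*SAP*

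**What the plan says.** The note under Figure F6 (SAP Appendix A) defines the plotted quantity: "point estimate is ratio of mean daily dose of each analgesia in each group". For the interval it says "95% CI calculated by using bootstrap estimation with 10,000 replications to estimate the standard error of the mean ratio". Neither the note nor Appendix B mentions a log scale, percentile limits or a bias-corrected interval.

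Appendix B obtains each average daily dose by "dividing the total dose (mg) for the entire hospital stay by the total number of days each analgesia was received". That quotient is undefined for a patient who never received the drug, so the natural reading is a mean among users. The display rule is "If less than 5% of the entire cohort received an analgesic agent, then this analgesic will be excluded from the summary figure".

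The F6 note does not name the numerator. Section 6.2.2 says "For all treatment comparisons, the open lobectomy group will be the reference group", which makes the ratio VATS to open. Section 8 records that version 2.0 dropped the adjustment of pain models for analgesia and adds: "Analgesia will be summarised by group instead".

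**The concern.** Using the replicates only to obtain a standard error discards the shape of the bootstrap distribution and imposes a symmetric interval on a skewed quantity. The standard error of a ratio grows with the ratio. The interval is therefore comparatively narrow when the observed ratio is below 1 and wide when it is above 1.

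With open as the reference, intervals that wrongly suggest VATS patients received less drug are more frequent than nominal, and those that wrongly suggest they received more are rarer. The figure will be read next to the pain scores, where the direction of any difference in analgesia matters. An interval that treats the two directions differently is a poor guide for that purpose.

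**Working it through.** The SAP states no error rate for F6, so there is no figure of its own to reproduce.

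**Inputs from the SAP.** Sample size: "The planned sample size for the VIOLET study is 498 patients". Allocation: "Patients are randomised (1:1 ratio) to either VATS lobectomy or open lobectomy". Display floor: 5% of the cohort. Smallest displayed group: 0.05 × 498 = 24.9 users, or 24.9 / 2 ≈ 12 per arm.

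**Assumptions, not in the SAP.** Lognormal doses, equal user numbers in the two arms, and dose CV of 0.3, 0.5 or 1.0.

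**Analytic check.** Let R be the ratio and s the standard error of log R. With n users per arm, s ≈ CV × √(2/n), and the standard error of R is about R × s. The literal interval is R(1 ± 1.96s); the log-scale interval is R × exp(±1.96s). For n = 25 and CV 1.0, s ≈ √(2/25) = 0.283 and 1.96s = 0.554.

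| Observed ratio | Literal interval | Log-scale interval |
|---|---|---|
| VATS:open = 2.0 | 0.89 to 3.11 | 1.15 to 3.48 |
| Same data as open:VATS = 0.5 | 0.22 to 0.78 | 0.29 to 0.87 |

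The literal interval includes 1 one way round and excludes it the other. The log-scale limits are reciprocals, so their reading does not change. The literal lower limit is negative once 1.96s > 1, that is s > 0.51; at 13 per arm and CV 1.5, s ≈ 1.5 × √(2/13) = 0.59.

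**Simulation, true ratio 1, users only.** Entries are the percentage of trials with the interval wholly below 1 / wholly above 1 (nominal 2.5 / 2.5).

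| Users per arm | CV | As written | Log scale |
|---|---|---|---|
| 12 | 0.3 | 5.5 / 2.8 | 4.0 / 4.2 |
| 12 | 0.5 | 6.4 / 1.6 | 4.0 / 4.0 |
| 12 | 1.0 | 7.8 / 0.7 | 4.9 / 4.4 |
| 25 | 0.5 | 4.6 / 1.7 | 3.1 / 3.4 |
| 25 | 1.0 | 6.8 / 0.7 | 3.4 / 3.7 |
| 50 | 0.5 | 3.7 / 2.0 | 2.6 / 3.2 |
| 50 | 1.0 | 5.5 / 1.0 | 3.4 / 3.0 |
| 249 | 0.5 | 2.9 / 2.0 | 2.5 / 2.4 |
| 249 | 1.0 | 3.8 / 1.5 | 2.8 / 2.5 |

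The row for 12 users and CV 1.0 used 3,000 trials with the plan's 10,000 replications; the others used 300 to 1,000 replications. At 3,000 trials the Monte Carlo standard error of a 5% rate is √(0.05 × 0.95 / 3,000) ≈ 0.4 points. Percentile limits gave nearly the same results as the log scale. Separate runs of the interval as written, at CV 1.0, gave 8.5 / 0.9 at 13 per arm, 6.6 / 0.9 at 25, 5.6 / 1.1 at 50 and 3.9 / 1.1 at 125.

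**Negative lower limits.** These occurred in about 10% of trials at 12 users per arm and CV 1.0.

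**If non-users count as zero (249 per arm).** The tails as written are 6.3 to 7.4 / 0.0 at 5% use and 4.4 to 5.1 / 0.8 to 0.9 at 40% use. At 5% use the lower limit is negative in 76 to 97% of trials.

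**The case against.** **F6 is descriptive.** Appendix B says the ratios are to be summarised, analgesic dose is not among the outcomes listed in section 6.2.2, and no test or decision attaches to the figure. This stands. It is also not the only analgesia output: Table T5 gives intra-operative analgesia by arm, and section 6.2.5 plans an analgesia-by-treatment interaction for pain scores. A reader might infer that the pain conclusions rest on F6; the SAP does not support that.

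**The apparent power loss is mostly an artefact.** At 13 per arm and CV 1.0, a true doubling in VATS gives an interval above 1 in about 20% of trials as written and 55% on the log scale. It is tempting to report a 35-point loss. However, the two intervals have very different upper-tail error (about 1% against more than 5%). With the upper tails matched, the comparison is about 37% against 44%.

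**Total error barely changes.** At 12 per arm and CV 1.0 it is 7.8 + 0.7 = 8.5% as written and 4.9 + 4.4 = 9.3% on the log scale. The change balances the tails; it does not restore 5% coverage error at this size.

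**The worst cells are chosen inputs.** User counts and dose CV are assumed, and Appendix B pools agents where it can, which raises the counts. This stands.

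**The text may already allow something better.** The note does not write out the symmetric formula, and the figure itself is not shown, so its axis may already be logarithmic. Section 1.4 calls the skeletons a guide, and section 6.2.4 promises checks of assumptions. But section 1.4 also asks for content consistent with Appendix A, and a general promise to check assumptions does not replace a stated interval rule. If another interval was intended, the note should say so.

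**Conclusion.** The point holds as a minor one. The literal rule gives an interval with unequal tails, a reading that depends on which arm is the numerator, and a lower limit that can be negative. At CV 1.0 the imbalance runs from roughly 8% / 1% at the display floor to about 4% / 1% at 125 users per arm. At the floor with CV 0.3 it is 5.5% / 2.8%, and it is small for drugs nearly everyone receives.

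The sizes rest on lognormal doses, an assumed CV, equal user numbers, the literal reading of the note, and VATS as numerator carried over from section 6.2.2. The direction was the same whether means were taken over users only or with zeros for non-users.

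The consequence is a directional bias in a supporting figure. No primary, secondary or safety comparison changes.

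**What to change.** Replace the last sentence of the F6 note with wording such as: the 95% CI is obtained by resampling patients within treatment group (10,000 replications) and taking percentile or BCa limits. An equivalent choice is the standard error of the log mean ratio, back-transformed. State that the ratio is VATS to open and show F6 on a log axis.

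If non-users are to count as zero, percentile limits are the safer choice. At 5% use, 193 to 196 of 1,500 simulated trials (about 13%) had at least one resample with no user in an arm, for which the log ratio is undefined.

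The cost is one sentence and a line of code, since the replicates are already generated. There are two downsides. At about 12 to 13 users per arm the limits still miss about 4 to 5% per tail. Detection of a true lower dose in VATS also falls somewhat: for a halving at 13 per arm and CV 1.0, from about 67% to 56%. Priority: optional.
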